# COPD Medication Class Categories

The following targeted COPD concomitant medications will be defined for descriptive summary of COPD concomitant medication use by class at Baseline and EOS or last contact. Baseline COPD concomitant medications will be medications with "On-Study Concomitant" status designated in the eCRF and a start date on or prior to the patient's Baseline date. EOS COPD concomitant medications will be medications designated "On-Study Concomitant" in the eCRF with a status of "Ongoing" at EOS or the latest medication entry.

*Targeted COPD Concomitant Medications* at Baseline and EOS (Patients could contribute to multiple categories)

- SABA only
- SAMA only
- SAMA + SABA (free or FDC)
- PDE4 Inhibitors
- Methylxanthines
- Oxygen

• Not taking any targeted COPD concomitant medications

The following Study COPD medication class categories will also be defined for descriptive summary of Study COPD medication at EOS or last contact:

Study COPD Medications at EOS (Categories are non-overlapping)

- LAMA only
- LABA only
- LAMA + LABA
- ICS + LABA
- ICS + LAMA + LABA
- ICS-LAMA-LABA (FDC)
- Not taking any Study COPD Medications
- Discontinued all COPD Treatment: Patients not taking any COPD medication at EOS (no Study COPD medication use and no targeted COPD concomitant medication use).

Additionally, the following definitions described below will descriptively report changes in Study COPD medication at EOS or last contact.

- **Original Randomized Treatment**: Patients taking the same COPD medication at EOS as originally initiated for randomized COPD study treatment.
  - Stiolto Respimat patients taking Stiolto Respimat.
  - Triple Therapy patients taking the same individual components of ICS plus LAMA plus LABA as initiated at Baseline.
- Step-Over In-Class Randomized Treatment: This definition only applies to patients taking different treatment components at EOS as originally initiated for their randomized COPD study treatment (i.e., those not considered "Original Randomized Treatment").
  - Triple Therapy patients taking any combination of ICS plus LABA plus LAMA that meets the study definition of triple therapy at EOS will be considered "Step-Over In-Class Randomized Treatment" if changed from original study medications.
  - Stiolto Respimat patients taking a LAMA plus LABA regimen at EOS other than Stiolto Respimat.
    - 4.4.3 CAT

#### 4.4.3.1 Overview

The CAT will be administered at Baseline. It is a short (8-item), simple, patient-completed questionnaire that measures the impact of COPD on a patient's well-being and daily life. Patients rate the following items on a 6-point (0-5) scale, where higher scores indicate worse

<sup>1 Jones PW, Harding G, Berry P, et al. Development and first validation of the COPD Assessment Test. Eur Respir J. 2009;34:648-654.

symptoms: Cough, Phlegm, Chest Tightness, Breathlessness, Activities at Home, Confidence Leaving Home, Sleep and Energy.

The CAT instrument is attached in Appendix C.

# 4.4.3.2 Scoring and Categorization

The CAT score will be calculated by summing responses from individual items, yielding scores ranging from 0-40, with higher scores indicating worse COPD-related health status. Total CAT scores will be descriptively summarized.

Total CAT scores will also be categorized as follows to enable Global Initiative for Chronic Obstructive Lung Disease (GOLD) A-D classification:

CAT < 10 $CAT \ge 10$ 

For further descriptive summary, total CAT score will also be categorized as follows:

CAT < 10 CAT 10 to 20 CAT 21 to 30 CAT 31 to 40

#### 4.4.3.3 Missing Data

The CAT score is calculated as the sum of the responses present. If more than two responses are missing, a score cannot be calculated; when one or two items are missing, their scores will be set to the average of the non-missing item scores.

#### 4.4.4 COPD and Exacerbation History

Years with COPD will be calculated using Baseline visit date and COPD diagnosis date.

COPD exacerbation history will be collected at Baseline as the number of moderate COPD exacerbations in the past year and the number of severe COPD exacerbations requiring hospitalization in the past year. To enable GOLD A-D classification, the number of prior moderate and severe COPD exacerbations in the past year will be categorized as follows:

- Moderate Exacerbations (did not lead to hospitalization):  $0, 1, \ge 2$
- Severe Exacerbation (lead to hospitalization):  $0, \ge 1$

Additionally, to enable classification of a high risk subgroup, the following exacerbation history category will be defined:

•  $\geq$  2 Moderate or Severe Exacerbations

# 4.4.5 GOLD A-D Classification

Patient's GOLD A-D classification will be defined at Baseline using CAT scores and exacerbation history as follows:

- GOLD A
  - CAT <10 AND
  - Moderate Exacerbation = 0 or 1 AND Severe Exacerbation = 0
- GOLD B
  - $\circ \quad CAT \ge 10 \text{ AND}$
  - Moderate Exacerbation = 0 or 1 AND Severe Exacerbation = 0
- GOLD C
  - CAT <10 AND
  - Moderate Exacerbation  $\geq 2$  **OR** Severe Exacerbation  $\geq 1$
- GOLD D
  - $\circ$  CAT  $\geq$  10 AND
  - Moderate Exacerbation  $\geq 2$  **OR** Severe Exacerbation  $\geq 1$

If a patient is missing either exacerbation history or CAT score is missing, then GOLD A-D will not be defined for that patient.

# 4.4.6 Baseline ICS Prior Use

Patients will be categorized by prior ICS use (yes/no) at Baseline. Baseline prior ICS use is defined as reporting any ICS use with a start date prior to baseline.

# 4.4.7 Blood Eosinophils

Baseline blood eosinophil level will be reported as an absolute count and also categorized as follows:

- <100 cells/uL
- 100 to <300 cells/uL
- 300 to <400 cells/uL
- $\geq$ 400 cells/uL

# 4.4.8 High Risk Classification

A subgroup of high risk patients with baseline blood eosinophil count  $\geq$ 300 cells/uL and at least two moderate or severe exacerbations in the 12 months prior to baseline will be identified.

# 4.5 Analysis Assessments

# 4.5.1 Primary Endpoint Assessment

The primary endpoint is time to first moderate or severe COPD exacerbation over the 12 month study period. This endpoint is based on eCRF data as defined below.

An exacerbation must have at least two of the following symptoms reported on the eCRF as

occurring for  $\geq$  3 days:

- Cough
- Sputum production (volume)
- Change in sputum color
- Wheezing
- Shortness of breath
- Chest tightness

Additionally, the exacerbation must have required at least one of the following treatments as reported on the eCRF:

- Exacerbation treated with antibiotics
- Exacerbation treated with systemic steroids
- Hospitalization associated with exacerbation

COPD exacerbations will be classified based on treatment categories above as follows:

Moderate: Exacerbation treated with antibiotics and/or systemic steroids, but did not have hospitalization associated with it.

Severe: Hospitalization associated with exacerbation.

Time to first moderate or severe COPD exacerbation will be based on the patient's baseline visit and onset of exacerbation date up to and including the time of the planned EOS visit at 12 months. If there is a discrepancy between patient report and hospital records for onset of a severe exacerbation, hospital records will be used.

In the event of multiple COPD exacerbations, those occurring within 7 days duration of each other will be collapsed into one exacerbation event for analysis. If the start date of a subsequent exacerbation occurs within 7 days of the determined end date of a previous exacerbation, these two exacerbations will be collapsed into one event for analysis. In this case, the onset date will be the start date of the first event and the severity classification will be based on the treatment associated with the most severe exacerbation within the collapsed event.

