- A complete blood count (CBC) including differential white cell count will be drawn at baseline. In the event that a CBC is not available at baseline, laboratory results within 12 months of baseline will be accepted.
- The COPD Assessment Test™ (CAT) symptom score will be assessed at baseline.
- Study physicians will collect patient data (exacerbations, targeted medication changes, selected adverse events (AEs) (AEs leading to study treatment discontinuation, dose modification, or trial withdrawal)) during any patient office visits or other patient contact during the 12 months the patient is on study and enter it via an electronic data capture (EDC) system. Any Serious Adverse Events (SAEs), including COPD exacerbation SAEs, will be collected via paper system.
- Clinical data collection at the EOS visit at 12 months will include exacerbations, targeted medication changes, selected AEs and any SAEs.
- [REDACTED]

Study Duration: Patients will be on study and followed for 12 months by the physician to collect clinical data. [REDACTED]

Patient Reported Outcomes (PROs): The CAT will be administered at baseline to provide a simple and reliable measure of health status in COPD and assist patients and their physicians in quantifying the impact of COPD on the patient's health at baseline.

Effectiveness Analysis: The primary effectiveness analysis will assess time to first moderate or severe COPD exacerbation (as prospectively collected in the eCRF) of Stiolto Respimat compared to triple therapy. A Cox proportional hazards model will be used to compare treatments.

Secondary/Sensitivity Analyses: As a secondary effectiveness objective, the annual rate of moderate or severe exacerbations will also be calculated and compared between treatment groups. Other secondary analyses include evaluation of severe COPD exacerbations for time to first exacerbation and annual rate, proportion of patients with moderate or severe COPD exacerbations, sensitivity analyses relating to exacerbation definition and source data, and sensitivity analyses relating to generalizability of the study population.

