2.1.1 Primary Objective Definitions

For the purpose of this study, a COPD exacerbation is defined as a complex of lower respiratory events/symptoms (increase or new onset) related to the underlying COPD, with duration of three days or more, requiring a prescription of antibiotics and/or systemic steroids and/or hospitalization.

A complex of lower respiratory events/symptoms is defined as at least two of the following:

- Shortness of breath
- Sputum production (volume)
- Change in sputum color
- Cough
- Wheezing
- Chest tightness

“Onset of exacerbation” will be defined by the onset of first recorded symptom. The “end of exacerbation” will be decided by the investigator based on clinical judgment.

Exacerbations will be classified as follows:

Moderate: Exacerbation requiring receipt of an exacerbation-related prescription of oral corticosteroids and/or antibiotic, but not requiring hospitalization

[figure not shown]
Severe: Exacerbation requiring COPD-related hospitalization

For hospitalizations associated with COPD exacerbation, the information collected should include the start date of all COPD-related hospitalizations, as well as the discharge date from the hospital or equivalent.

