6.6 Safety Analysis

[figure not shown]
Collection of AEs in the study eCRF will be limited to AEs leading to study treatment discontinuation or dose modification, or trial withdrawal. All SAEs will be reported by the investigator via a dedicated SAE report form directly to Boehringer Ingelheim Global Pharmacovigilance as described in [section 7.2](#). As hospitalization SAEs are reflected in claims records, a patient-level review comparing hospitalization claims entries with reported SAEs for each respective patient will take place after completion of the 12-month visit in order to identify any hospitalizations of which the investigator was potentially unaware. The investigator will receive information of any SAE identified through this process and report it using the standard SAE reporting process (See [section 7.2](#)).

SAE data for analysis will be drawn from the Boehringer Ingelheim Safety Database.

Analysis of non-serious AEs (leading to study treatment discontinuation or dose modification, or trial withdrawal) will be performed on the study database, as these are entered in the eCRF only.

Safety analyses will be descriptive in nature. No hypothesis testing is planned prospectively.

AEs will be coded using the current version of the Medical Dictionary for Regulatory Activities (MedDRA) coding dictionary at the time of reporting, and recoded to the MedDRA version current at the time of database integration. Summary tables and listings will be produced to compare the incidence of AEs across treatment groups, by Preferred Term (PT)/System Organ Class (SOC) and also by medical concept (MedDRA Standardized Medical Queries (SMQ) or custom Boehringer Ingelheim searches termed Pharmacovigilance (PV) endpoints). All AEs with an onset after the first dose of trial medication and up to 21 days after the last dose of trial medication will be assigned to the on-treatment period. Other AEs will be assigned either to the screening period, post-treatment period or the post-study period as appropriate.

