7.2 SAEs

A SAE is defined as any AE which fulfils at least one of the following criteria:

- Results in death
- Is life-threatening, which refers to an event in which the patient was at risk of death at the time of the event; it does not refer to an event that hypothetically might have caused death if more severe
- Requires inpatient hospitalization, or
- Requires prolongation of existing hospitalization
- Results in persistent or significant disability or incapacity, or
- Is a congenital anomaly or birth defect, or
- Is deemed serious for any other reason if it is an important medical event when based on appropriate medical judgment which may jeopardize the patient and may require medical or surgical intervention to prevent one of the other outcomes listed in the above definitions.

AEs considered “Always Serious”

In accordance with the European Medicines Agency (EMA) initiative on Important Medical Events, Boehringer Ingelheim has set up a list of further AEs, which by their nature, can always be considered to be “serious” even though they may not have met the criteria of an SAE as given above. The investigators will be notified of any AE that is entered in the eCRF that meets criteria as an Important Medical Event per Always Serious List. The investigator will promptly complete the SAE form with all available information about the AE(s) and report to the sponsor’s unique entry point as described in the Investigator Site File (ISF) immediately (within 24 hours).

All SAEs will be reported via Boehringer Ingelheim SAE reporting forms to the Global Pharmacovigilance Database. If patient-level review of claims versus site entries reveals any hospitalization SAE in claims not already captured by the investigator, the investigator will be contacted providing information and asking for completion of an SAE form with those details known to him/her.

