7.2.1 Reporting Period of SAEs

AEs and SAEs will be reported from the time a patient signs consent until the final visit at 12 months or until the patient discontinues the trial. After the patient completes or discontinues the trial, the investigator does not need to actively monitor the patient for AEs but should only report related SAEs of which the investigator may become aware of by any means of contact with the patient, e.g. phone call.

SAE reporting procedure will follow usual Boehringer Ingelheim forms and processes and will be further described in the ISF. The investigator must report SAEs on a Boehringer Ingelheim SAE form via the fax form immediately (within 24 hours of investigator’s awareness of the

event) as described in the ISF. The same timeline applies if follow up information becomes available.

Healthcare Claims Database SAE reporting process

If patient level review of claims database versus site entries at '12+3 month mark' (3 months after the 12 month follow-up visit) reveals any hospitalization in claims database that is not already captured by the investigator as an SAE, the investigator will be contacted with this information. The investigator will promptly complete the SAE form with all available information about the patient's hospitalization and report to the sponsor's unique entry point as described in the ISF immediately (within 24 hours).

Information required

For each AE, the Investigator should provide the information requested on the appropriate eCRF pages (if applicable) and Boehringer Ingelheim SAE Report form. The Investigator should determine the causal relationship to the trial medication.

The following should also be recorded as S(AE) in the eCRF and SAE form (if applicable):

- Worsening of pre-existing conditions,
- Changes in vital signs, electrocardiograms (ECGs), physical examinations, and laboratory test results, if they are judged clinically relevant by the Investigator.

If such abnormalities already pre-exist prior to trial inclusion they will be considered as baseline conditions.

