# 6.4.1 AE Analysis

AE analyses will be descriptive in nature. No hypothesis testing is planned prospectively. All analyses of AEs will be based on the number of patients with AEs and NOT on the number of AEs.

SAE data will be drawn from the Boehringer Ingelheim Safety Database, while other AEs collected as per protocol through the eCRF will be drawn from the study database. AE data for analysis will be merged from all sources for analysis.

AEs will be coded using the current version of the Medical Dictionary for Regulatory Activities (MedDRA) coding dictionary at the time of reporting. Summary tables and listings will be produced to compare the incidence of AEs across treatment groups, by Preferred Term (PT)/System Organ Class (SOC).

The frequency and percentage patients experiencing AEs and SAEs will be summarized by SOC and PT for the safety population overall and by treatment group as follows:

- All collected AEs, regardless of seriousness, relatedness, or collection context
- AEs leading to study treatment discontinuation, dose modification or trial withdrawal
- AEs leading to study treatment discontinuation (subset of the above table)
- AEs with a reasonable causal relationship to study treatment
- All SAEs
- Fatal AEs (subset of all SAEs)
- Listing of all SAEs

There will be no subgroup analyses for safety.

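### Can a COPD admission that reaches the sponsor only through the claims review or an SAE form drop out of the severe-exacerbation endpoints?

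*SAP*

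**What the plan says.** **Endpoint source.** SAP 4.5.1 says of the primary endpoint: "This endpoint is based on eCRF data as defined below". It requires both the symptoms and the treatment to be reported on the eCRF. SAP 4.5.2, 5.5.3 and 5.5.3.2 carry the eCRF source over to the secondary endpoints, including both that count severe events alone. The protocol's definition (2.1.1) is "Severe: Exacerbation requiring COPD-related hospitalization".

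**SAE channel.** The protocol synopsis says: "Any Serious Adverse Events (SAEs), including COPD exacerbation SAEs, will be collected via paper system". For the safety tables, SAP 6.4.1 says: "SAE data will be drawn from the Boehringer Ingelheim Safety Database, while other AEs collected as per protocol through the eCRF".

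**Claims review.** Protocol 6.6 compares hospitalization claims with reported SAEs "in order to identify any hospitalizations of which the investigator was potentially unaware". Under Protocol 7.2.1 the trigger is that the review "reveals any hospitalization in claims database that is not already captured by the investigator as an SAE". Protocol 7.2 gives the consequence: "the investigator will be contacted providing information and asking for completion of an SAE form with those details known to him/her".

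**Site duties and cleaning.** For each AE, Protocol 7.2.1 asks for information on "the appropriate eCRF pages (if applicable) and Boehringer Ingelheim SAE Report form". Protocol 2.1.1 asks for admission and discharge dates of COPD-related hospitalizations. Protocol 5.4 counts contact with other physicians and receipt of records as sources of exacerbation data, and 8.1 gives the physician final responsibility for accurate, complete eCRFs. Protocol 8.3 and 8.4 assign cleaning, listing review and site queries to a data management plan.

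**The concern.** Two streams of information about the same admission run side by side, and the visible text does not join them. The endpoint stream is the exacerbation eCRF. The safety stream is the SAE form, supplemented by claims. The claims review is checked against the safety stream and feeds back into it. An admission already reported as an SAE but never entered as an exacerbation would therefore trigger nothing. One found in claims would prompt an SAE form but no stated exacerbation entry.

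The design makes such admissions plausible: only the baseline and 12-month visits are required, and the claims review exists because some admissions may be unknown to the investigator. Time to first severe exacerbation and the annual severe rate rest on admissions alone, and the events are likely to be few. Protocol 6.4 names claims-only and integrated eCRF/claims analyses for the primary endpoint, but the visible text names none for the severe endpoints. If events were lost more often in one arm, the severe hazard ratio and rate ratio would be biased. If they were lost equally, the intervals would be wider and the absolute rates too low.

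**Working it through.** **1. What the passages establish**

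- The severe endpoints use eCRF events only (SAP 4.5.2, 5.5.3, 5.5.3.2). This is explicit.
- The claims review is compared with SAEs, and its stated output is an SAE form (Protocol 6.6, 7.2, 7.2.1). This is explicit.
- Nothing forbids entering such an admission on the eCRF. Protocol 5.4 and 8.1 point towards entering it, and 7.2.1 mentions eCRF pages where applicable.
- A claims hit is a hospitalization from any cause. It becomes a severe exacerbation only if it is COPD-related and meets the SAP 4.5.1 symptom rule. Only some hits are relevant.
- SAP 5.5.3.3 speaks of including all severe exacerbations in the observation period, but the sentence goes on to patients who switch or stop treatment. It concerns treatment changes and does not promise complete ascertainment.

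**2. Checking the event model against the plan's own figure**

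Inputs (Protocol 6.3.1): margin 1.20, true HR 1.0, one-sided alpha 0.025, power 90%, 42.5% with an event in 12 months, 15% drop-out.

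- Events = 4 × (1.960 + 1.282)² / (ln 1.2)² = 1264.4, against 1264 in Table 2.
- With exponential event and drop-out times, c = −ln(0.85) = 0.1625 and h = −ln(1 − 0.425) = 0.5534. The observed fraction is h/(h + c) × (1 − exp(−(h + c))) = 0.3952.
- N = 1264.4 / 0.3952 = 3199, against 3200. The model reproduces the plan.

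**3. Severe events at the actual size of 703 (SAP 4.2)**

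The documents give no severe-event risk, no miss rate and no claims-linked share. The assumed ranges are:

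- 3-15% of patients with any severe event in 12 months;
- 25-100% of patients claims-linked;
- 5-20% of qualifying admissions in linked patients missing from the eCRF.

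Expected patients with an event, by the formula in step 2:

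- 3%: 0.0277 × 703 = 19.5
- 15%: 97.5

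Lost share k = miss rate × linked share, from 0.05 × 0.25 = 1.25% to 0.20 × 1.00 = 20%. Patients lost: from 19.5 × 0.0125 = 0.24 to 97.5 × 0.20 = 19.5.

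**4. Equal loss in both arms**

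The SE factor is 1/√(1 − k), from 1.006 to 1.118. The upper 95% limit at HR 1.0 is exp(1.96 × 2/√(d(1 − k))):

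| Events d | No loss | 1.25% lost | 20% lost |
|---|---|---|---|
| 19.5 | 2.431 | 2.445 | 2.700 |
| 97.5 | 1.487 | 1.491 | 1.559 |

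The hazard ratio itself stays about where it was.

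**5. Unequal loss (illustration only)**

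- With 10% missing in one arm and 5% in the other, and linked share L, the HR is multiplied by (1 − 0.10L)/(1 − 0.05L). That is 0.987 at L = 25% and 0.947 at L = 100%; with the arms reversed, 1.013 and 1.056.
- Even with 97.5 events and no loss, the interval runs from 1/1.487 = 0.67 to 1.487 around HR 1.0, so these shifts lie well inside it.
- A harsher contrast, 10% against 30% of all events, would multiply the HR by 0.9/0.7 = 1.29, or 0.7/0.9 = 0.78 when reversed. That would matter, but nothing in the documents points to it.

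Steps 3 and 4 count only losses that the claims review could recover. SAE-form events never entered on the eCRF for patients without claims data would come on top.

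**The case for a change.** The strongest case for acting is that each step of the literal reading is right. None of the passages on the other side closes the gap completely. Receipt of records and the duty of completeness permit late entry but do not check for it. The eCRF-pages phrase is qualified and does not name the exacerbation page. The hospital-records rule in SAP 4.5.1 settles an onset date and cannot add a missing event. The merging in SAP 6.4.1 is of AE data. Since no test is planned (SAP 2.1), the estimates and intervals are all that the severe endpoints deliver. A pre-lock match, a flag and a supplementary table would be cheap. The last claims review should also have come in time: enrolment closed at the end of August 2019, and adding 12 + 3 months gives about the end of November 2020, before SAP version 3.0 (March 2021).

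What stands is that the matching step is not stated in the visible text. That it was not planned does not follow:

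- The data management plan, where such a step belongs, is not in the file.
- The SAP sections where severe-event claims analyses could sit are withheld. SAP 2.1 cites a section 4.5.4.3 that is not shown, and the numbering passes from 5.5.1 to 5.5.3.
- Protocol 6.4 is visibly incomplete too, since 6.2.1.2 places an on-treatment sensitivity analysis there that does not appear.
- The synopsis promises sensitivity analyses on source data directly after listing the severe endpoints, without limiting them to the primary endpoint.

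The gain from a supplementary analysis is also doubtful. A claims prompt reaches only linked patients. Symptoms would be confirmed in retrospect by investigators who know the treatment. The eCRF result would remain the main analysis in any case.

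**Conclusion.** No change to the plan follows. The gap is one that data managers and analysts fill sensibly. A physician told of a COPD admission already has a duty to complete the eCRF, and matching SAEs to the clinical data is ordinary cleaning work that the protocol leaves to the data management plan. Using prospective site data as the single endpoint source is a declared and defensible choice. SAP 6.4.1 also reports SAEs by arm, so a gross mismatch between COPD admissions and severe exacerbations could be noticed, although SAP 6.3 limits those tables to on-treatment events.

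The effect rests entirely on assumed severe risk, miss rate and linked share: about 0.2-20 patients, and an SE factor of 1.006-1.118 under equal loss. Bias needs loss that differs by arm. Open-label treatment makes that possible, but no passage gives a mechanism for it, and no non-inferiority decision or p-value depends on the result. The judgement would change only if the data management plan proved to contain no such check and the unmatched admissions turned out unequal between the arms. The available documents show neither.
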